3.6.3 Additional safety assessments

3.6.3.1 Laboratory variables, vital signs and electrocardiograms (ECGs)

The following laboratory variables, vital signs and electrocardiogram (ECG) variables will be analyzed. They will be converted into standard international units and conventional unit, if applicable.

- Hematology:
 - Red blood cells and platelets and coagulation: hemoglobin, hematocrit, mean corpuscular volume, mean corpuscular hemoglobin, red blood cell count, platelet count
 - White blood cells: white blood cell count, neutrophils, lymphocytes, monocytes, basophils, eosinophils

- Clinical chemistry:
 - Metabolism: glucose, total protein, albumin, creatine phosphokinase
 - Electrolytes: sodium, potassium, calcium
 - Renal function: creatinine, blood urea nitrogen
 - Liver function: alanine aminotransferase, aspartate aminotransferase, alkaline phosphatase, total and direct bilirubin
 - Pregnancy test: Serum β -human chorionic gonadotropin (all female participants)
 - Hepatitis screen: human immunodeficiency virus antibody, hepatitis B surface antigen, hepatitis C virus antibody
- Urinalysis:
 - Urinalysis for quantitative analysis: pH, specific gravity, proteins, glucose, blood, ketones, bilirubin, urobilinogen, nitrite, leukocyte esterase (by dipstick)
- Vital signs: heart rate, systolic and diastolic blood pressure, weight, respiratory rate, temperature
- ECG variables: heart rate, PR, QRS, QT, and corrected QTc (according to Bazett and Fridericia)

Data below the lower limit of quantitation/detection limit (LLOQ) will be replaced by half of the LLOQ, data above the upper limit of quantification (ULOQ) will be replaced by ULOQ value for quantitative analysis.

Quantitative analyses

When relevant, for laboratory variables, vital signs and ECG variables above, descriptive statistics for results and changes from baseline will be provided for each analysis visit window during the on-treatment period for Part A and Part A + Part B. These analyses will be performed using central measurements only (when available) for laboratory variables.

For each laboratory parameter, vital sign parameter and ECG parameter, mean changes from baseline with the corresponding standard error will be plotted over time.

Analyses according to PCSA

Potentially clinically significant abnormality (PCSA) analyses will be performed based on the PCSA list currently in effect at Sanofi at the time of the database lock. For parameters for which no PCSA criteria are defined, similar analyses will be done using the normal range, if applicable.

Analyses according to PCSA (normal range) will be performed based on the worst value during the treatment-emergent period, using all measurements (either local or central, either scheduled, nonscheduled or repeated).

For laboratory variables, vital signs and ECG variables above, the incidence of participants with at least one PCSA during the on-treatment period for Part A and Part A + Part B will be summarized regardless of the baseline level and according to the following baseline status categories:

- Normal/missing
- Abnormal according to PCSA (normal range) criterion or criteria

Additional analyses for drug-induced liver injury

The following additional analyses will be performed for drug-induced liver injury in Part A and Part A + Part B:

- Time to onset of the initial ALT elevation $>3 \times$ ULN, the initial AST elevation $>3 \times$ ULN, and the initial ALT or AST elevation $>3 \times$ ULN with total bilirubin elevation $>2 \times$ ULN during the treatment-emergent period will be presented by treatment group with Kaplan-Meier curves.
- A graph of the distribution of peak values of ALT versus peak values of total bilirubin during the treatment-emergent period will be provided.
- For each liver function test (eg, ALT), participants having experienced a PCSA (eg, ALT >5 ULN) will be summarized using the following categories: Returned to baseline PCSA status (or returned to value \leq ULN in case of missing baseline) before last IMP dose, Returned to baseline PCSA status after last IMP dose, Never returned to baseline PCSA status, No assessment after elevation. This summary will be performed by categories of elevation (ALT $>3, >5, >10, >20$ ULN).

3.6.3.2 Analysis of suicidality assessment

The number (%) of participants with suicidal ideation, suicidal behavior, and self-injurious behavior without suicidal intent based on the C-SSRS during treatment will be summarized. A shift table for baseline versus during treatment responses in Part A and Part A + Part B will be provided according to the categories of no suicidal ideation or behavior, suicidal ideation and suicidal behavior.

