5.2 EXCLUSION CRITERIA

Participants are excluded from the study if any of the following criteria apply:

Medical conditions

E 01. Participants with immunodeficiency syndromes or other autoimmune diseases requiring immunosuppressive therapy.

E 02. Participants with a history of seizures or epilepsy (history of febrile seizure during childhood is allowed).

E 03. Participants with known clinical relapse (acute or subacute episodes of new or increasing neurological dysfunction followed by full or partial recovery, in absence of fever or infection) within 8 weeks of screening ([1](#)).

- E 04. Participants with a neurological disease history other than MS, eg, head trauma within 3 months, cerebrovascular disease, and vascular dementia.
- E 05. Participants with a history of recent serious infection (eg, pneumonia, septicemia) within 4 weeks of screening; an infection requiring hospitalization or intravenous antibiotics, antivirals, or antifungals within 4 weeks of screening; or chronic bacterial infections (such as tuberculosis) deemed unacceptable, as per Investigator's judgment.
- E 06. Participants who have significant cognitive impairment, psychiatric disease, other neurodegenerative disorders (eg, Parkinson disease or Alzheimer disease), substance abuse (including a history of alcohol abuse), or any other conditions that would make the participants unsuitable for participating in the study or could interfere with assessment or completing the study in the opinion of the Investigator.
- E 07. Participants with a documented history of attempted suicide over the 24 weeks prior to the Screening Visit, presents with suicidal ideation of category 4 or 5 on the Columbia Suicide Severity Rating Scale (C-SSRS), or if in the Investigator's judgment, the participant is at risk for a suicide attempt.
- E 08. Participants with a history of unstable or severe cardiac, pulmonary, oncological, hepatic, or renal disease or another medically significant illness other than MS precluding their safe participation in this study.
- E 09. Participants who received a live vaccine within 14 days before the Screening Visit.
- E 10. Participants with a known history of allergy to any ingredients of SAR443820 (mannitol, lactose monohydrate, sodium starch glycolate, colloidal silicon dioxide, magnesium stearate, hypromellose, titanium dioxide, polyethylene glycol, and microcrystalline cellulose).

Prior/concomitant therapy

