8.2.7 Suicidal ideation and behavior risk monitoring

SAR443820 crosses the blood-brain barrier. Assessment of suicidal ideation and behavior/treatment-emergent suicidal ideation and behavior will be monitored during ACT16753 using the C-SSRS. For safety reasons, the C-SSRS will be administered throughout the study by the Investigator or delegated to an individual who is certified to administer the scale.

Study intervention administration must be interrupted if a participant scores “yes” on item 4 or 5 of the Suicidal Ideation Section of the C-SSRS or “yes” on any item of the Suicidal Behavior Section. A mental health professional will be consulted and will decide whether the study intervention can be restarted and if any additional risk mitigation strategies are required (eg, increased monitoring, antidepressant administration).

Participants being treated with the study intervention should be monitored appropriately and observed closely for suicidal ideation and behavior (SIB) or any other unusual changes in behavior, especially at the beginning and end of the course of intervention, or at the time of dose changes, either increases or decreases. Participants who experience signs of SIB, should undergo a risk assessment. All factors contributing to SIB should be evaluated and consideration should be given to discontinuation of the study intervention.

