- Intensive treatment in an emergency room or at home for:
 - Allergic bronchospasm
 - Blood dyscrasias (ie, agranulocytosis, aplastic anemia, bone marrow aplasia, myelodysplasia, pancytopenia, etc)
 - Convulsions (seizures, epilepsy, epileptic fit, absence, etc).
- Development of drug dependence or drug abuse
- ALT $>3 \times$ ULN + total bilirubin $>2 \times$ ULN or asymptomatic ALT increase $>10 \times$ ULN
- Suicide attempt or any event suggestive of suicidality
- Syncope, loss of consciousness (except if documented as a consequence of blood sampling)
- Bullous cutaneous eruptions

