3 STATISTICAL ANALYSES

3.1 GENERAL CONSIDERATIONS

In general, continuous data will be summarized using the number of observations available, mean, standard deviation (SD), median, interquartile range (Q1, Q3), minimum, and maximum.

Categorical and ordinal data will be summarized using the count and percentage of participants.

Efficacy data will be analyzed in the randomized and treated population except the primary endpoint which will be analyzed in the mITT population, and safety data will be analyzed in the safety population, unless specified otherwise.

In Part A, baseline values are defined as follows. The baseline value of NfL is defined as the lower value of screening and Day 1 visits if the number of gd-enhancing T1 lesion at Day 1 is greater than zero, otherwise it will be the average values of the assessments on screening and Day 1 visits prior to the first dose of the study intervention. The baseline values of EDSS and PD biomarkers other than NfL are defined as the average of the screening and Day 1 visit values prior to the first dose of the study intervention. If one of the values for the above assessments at screening and Day 1 is missing, the non-missing value will be used as the baseline value. For the other efficacy and safety assessments, the baseline values are defined as the last available value before the first dose of the study intervention. For the C-SSRS, the baseline value will be the worst assessment between the past 6 months evaluation at screening and the since last visit evaluation on Day 1. For participants randomized but not treated, the baseline value is defined as the last available value before randomization. Unless otherwise indicated, 2-sided p-values and 95% confidence intervals [CI(s)] will be provided for efficacy assessment of treatment differences. Unless otherwise specified, analyses will be performed by initial intervention group, ie, placebo or SAR443820 20 mg QD (and overall for baseline and demographics characteristics).

In Part B, efficacy analyses will be conducted accumulatively according to the treatment group allocated by randomization in Part A (ie, placebo/SAR443820 20 mg QD versus SAR443820 20 mg QD/ SAR443820 20 mg QD). Baseline values defined above for Part A will be used as the baseline in the efficacy analyses for Part B, unless otherwise noted. Safety analyses in Part B are specified in [Section 3.6](#).

Observation period

The observation period for safety will be divided into 4 segments:

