3.6 SAFETY ANALYSES

All safety analyses will be performed on the safety population as defined in [Section 2](#), unless otherwise specified, using the following common rules:

- The analysis of the safety variables will be essentially descriptive, and no testing is planned.
- Safety data in participants who do not belong to the safety population (eg, exposed but not randomized) will be provided separately.

In Part A, the safety analyses will be carried out with participants by the actual treatment received, irrespective of the treatment the participant has been randomized to.

Part A + Part B Safety Analyses

For categorical safety measures, such as AE, PCSA, shift summaries, data throughout both Part A and Part B will be summarized in three groups:

- Placebo/SAR443820 group includes participants who actually received placebo in Part A and SAR443820 in Part B. For participants in this group, only the data during SAR443820 exposure in Part B will be summarized. The baseline will be defined as the last available value prior to the first dose of SAR443820 in Part B.
- SAR443820/SAR443820 group includes participants who actually received SAR443820 in Part A, regardless of whether they entered Part B. For participants in this group, all data during SAR443820 exposure will be summarized. The baseline will be defined as the last available value prior to the first dose of the study intervention (same baseline defined for Part A in [Section 3.1](#)).
- Overall SAR443820 group includes participants from Placebo/SAR443820 group and SAR443820/SAR443820 group.

For continuous safety measures collected at longitudinal time point, such as labs and vital signs, data throughout both Part A and Part B will be summarized in two groups:

- Placebo/SAR443820 group includes participants who actually received placebo in Part A, regardless of whether they enter Part B. For participants in this group, all data during the on-treatment period of Part A and Part B will be summarized at each protocol scheduled visit. The baseline will be defined as the last available value prior to the first dose of study intervention (same baseline defined for Part A in [Section 3.1](#)).

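### The C-SSRS outputs treat suicidal ideation as one class, so the shift table shows worsening from items 1-3 to item 4 or 5 as no change

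*SAP*

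**What the plan says.** SAP 3.6.3.2 plans two C-SSRS outputs.

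- A count summary: "The number (%) of participants with suicidal ideation, suicidal behavior, and self-injurious behavior without suicidal intent based on the C-SSRS during treatment".
- A shift table from baseline to on-treatment responses, for Part A and for Part A + Part B, "according to the categories of no suicidal ideation or behavior, suicidal ideation and suicidal behavior".

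The protocol uses a finer scale. Under Protocol 8.2.7, "Study intervention administration must be interrupted if a participant scores" positive "on item 4 or 5 of the Suicidal Ideation Section of the C-SSRS", or positive on any item of the behavior section. A mental health professional then decides on restart. Exclusion criterion E 07 (Protocol 5.2) uses the same cut-off at entry: it bars a participant who "presents with suicidal ideation of category 4 or 5 on the Columbia Suicide Severity Rating Scale (C-SSRS"), and also anyone with a documented attempt in the 24 weeks before screening or judged by the investigator to be at risk of an attempt.

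Two baseline rules bear on the shift table. SAP 3.1 has a rule specific to the C-SSRS: "the baseline value will be the worst assessment between the past 6 months evaluation at screening" and the Day 1 evaluation. SAP 3.6, for categorical safety measures including shift summaries over Part A + Part B, says of the placebo/SAR443820 group: "The baseline will be defined as the last available value prior to the first dose of SAR443820 in Part B".

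**The concern.** Protocol 8.2.7 gives penetration of the blood-brain barrier as the context for C-SSRS monitoring, and both the entry criterion and the interruption rule turn on ideation item 4 or 5. The SAP then merges everything below and above that line. Lower-level ideation is not excluded by category, and the SAP 3.1 baseline takes the worse of a six-month look-back and Day 1, so the ideation row of the shift table can be populated at baseline. Within that row, the change that the protocol treats as serious enough to interrupt treatment does not register as a shift.

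What is at stake is the reader's ability to compare arms on the ideation part of the protocol's own threshold from the C-SSRS tables. The primary endpoint is not touched, and neither is the protection of individual participants, because the 8.2.7 rule applies whatever the table shows.

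**Working it through.** The plan gives no figure to reproduce. The check is to map each possible transition onto the three SAP categories and compare the result with the 8.2.7 trigger. The documents name only items 4 and 5; items 1-3 are inferred from the numbering.

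| Baseline | Worst on treatment | Cell in SAP table | Shown as a shift? | 8.2.7 trigger met? |
|---|---|---|---|---|
| Items 1-3 | Items 1-3 | ideation to ideation | No | No |
| Items 1-3 | Item 4 or 5 | ideation to ideation | No | Yes |
| None | Items 1-3 | none to ideation | Yes | No |
| None | Item 4 or 5 | none to ideation | Yes | Yes |
| None or ideation | Behavior | to behavior | Yes | Yes |

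Rows 1 and 2 share a cell although they differ on the trigger, and so do rows 3 and 4. Row 5 is shown correctly. With ideation split at items 1-3 and 4-5 the table becomes 4 × 4: row 2 moves off the diagonal, and rows 3 and 4 separate.

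**Do other planned outputs fill the gap?**

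- The n (%) summary in SAP 3.6.3.2 has the same single ideation class.
- Suicidality is not among the AESIs in Protocol 8.3.9 or SAP Table 6.
- SAP 3.6.2 tabulates TEAEs leading to permanent discontinuation. The C-SSRS trigger leads to an interruption that may end in a restart. Protocol 7.1.3 has the duration of interruptions recorded, but the SAP plans no table of them, and exposure in SAP 3.6.1 is calculated without regard to them.
- AE and SAE tables may contain the case (see the objection), but they do not tabulate C-SSRS scores.

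**Size.** Neither document gives a rate of baseline ideation or of worsening to item 4 or 5. For illustration only, assume that 5% to 15% of the planned 84 participants per arm have baseline ideation: 0.05 × 84 = 4.2 and 0.15 × 84 = 12.6, or about 4 to 13 per arm. These are participants who could be misclassified if they worsened. The number actually hidden would be this count times an unknown probability of reaching item 4 or 5.

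**Baseline in Part A + Part B.** Take a placebo participant with lower-level ideation in the six months before screening and none at the last assessment before Part B. Under SAP 3.1 the baseline category is ideation; under the SAP 3.6 reset it is none. Item 4 or 5 in Part B is then no shift under one rule and a shift under the other. SAP 3.6.3.2 does not say which rule governs.

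**The case against.** The strongest reply is that the event has other routes into the report. Protocol 10.3.1 counts clinically significant abnormal safety assessments as AEs and gives a resulting discontinuation or dosing change as an example. Protocol 10.3.2 lists "Suicide attempt or any event suggestive of suicidality" among medically important events. SAP 3.6.2 then tabulates TEAEs and treatment-emergent SAEs and lists SAEs and severe AEs, and worsening on treatment counts as treatment-emergent. The DMC also sees unblinded safety data. Further, suicidality is not an AESI or a listed risk, the safety analysis is descriptive, and 8.2.7 is a rule for managing participants that makes no promise about tables.

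Much of this stands, and it rules out stronger readings that a reader might infer:

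- *An arm difference in item 4-5 ideation would be invisible.* Not supported. It is hidden in the C-SSRS tables; cases may still appear as AEs or SAEs.
- *No C-SSRS output reflects the interruption threshold.* Not supported. The behavior part of the trigger is reported separately in both outputs; only the item 4-5 part is missing.
- *Some 4 to 13 participants per arm are affected.* Not supported. That range rests on an assumed prevalence and is only a denominator at risk. The other parts of E 07, and E 06 on psychiatric disease that makes a participant unsuitable, would reduce it.

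What the reply does not do is supply the missing comparison. The AE and SAE route depends on investigator judgment and coding and gives no count by arm of participants scoring item 4 or 5. Nor is finer grading foreign to this SAP: section 3.6.3.1 summarizes liver elevations at ALT >3, >5, >10 and >20 ULN.

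**Conclusion.** The point holds as a reporting gap in a descriptive safety analysis. By the definition of its categories, the shift table cannot show worsening from items 1-3 to item 4 or 5, and for participants with no baseline ideation it cannot tell item 1 from item 5. No planned C-SSRS tabulation gives item 4-5 ideation by arm. This follows from the category definitions alone and needs no assumed prevalence; it does assume that item-level scores are available, as applying 8.2.7 requires. How many participants are involved cannot be derived from the documents, and it may be few. The change is worth making because it is nearly free and lets the tables show a threshold that the protocol already uses.

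**What to change.** In SAP 3.6.3.2:

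1. Use four ordered shift categories: no ideation or behavior; ideation items 1-3; ideation item 4 or 5; suicidal behavior.
2. Make the same split of ideation in the n (%) summary.
3. Add the n (%) per arm meeting the Protocol 8.2.7 threshold (item 4 or 5, or any behavior item), for Part A and Part A + Part B.
4. State whether the SAP 3.1 or the SAP 3.6 baseline applies to placebo/SAR443820 participants in the Part A + Part B shift table.

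The cost is SAP wording, one extra row and column, and one added line. Some cells will hold small counts, which is acceptable in a descriptive table. No new assessment is needed, since sites must already score items 4 and 5, and no clinical rule changes.

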3.7 OTHER ANALYSES

3.7.1 Pharmacokinetic (PK) analyses

Plasma concentration of SAR443820 will be summarized by study intervention in the PK population using arithmetic and geometric means, standard deviation, standard error of the mean, coefficient of variation, minimum, median and maximum per sampling time. For drug-treated participants, where concentration values are below the lower limit of quantification (LLOQ), one-half of the LLOQ will be used. Values will be expressed in the tables with no more than three decimal places. These analyses will be performed for all participants received SAR443820 and by baseline body weight (by quartiles).

The population PK analyses will be presented separately from the main clinical study report.

3.7.2 Pharmacodynamic (PD) analyses

PD parameters include sNfL, CHI3L1, sGFAP (excluding China), IL1 β , IL6, IL8, TNF α , CCL3 and CCL4. NfL data will be analyzed under primary endpoint as described in Section 3.2. The rest of PD parameters will be summarized in Part A by actual treatment group in the safety population using the following descriptive statistics: mean, geometric mean, median, standard deviation, coefficient of variation, minimum, and maximum. The corresponding change from baseline values will also be provided. Plots of mean (\pm SD) and/or mean change (\pm SD) over time will also be provided for better visualization.

3.8 INTERIM ANALYSES

No interim analysis is planned.

4 SAMPLE SIZE DETERMINATION

Sample size calculations were performed to ensure reasonable accuracy for the estimation of the ratio of the SAR443820 arm sNfL geometric mean relative to the placebo arm sNfL geometric mean. The width (when a GMR of █ is observed, which corresponds to a 30% reduction relative to placebo) of the 2-sided 90% CI, using a coverage correction to ensure coverage probability of █%, is displayed for various sample sizes in [Table 7](#):

Table 7 - Sample size determination

N	Log-transformed data			Corresponding geometric mean ratio (GMR)					
	Difference in means	Standard deviation (SD)	90% confidence interval (CI) half width*	Lower limit	Upper limit	GMR	Lower limit	Upper limit	Total width (asymmetric)
█	█	█	█	█	█	█	█	█	█

(*): with a coverage probability (probability that the observed interval will be no longer than the specified width) of 90%.

For an observed █ reduction relative to placebo, a sample size of 168 participants (to account for an anticipated 17% dropout rate) will provide an upper limit below 0.90 (10% of reduction) for the 2-sided 90% CI, which is deemed sufficient.

